3.2. Study Matrix

Components	Objectives	Tasks
Case-control study	Primary + Secondary	See study matrix below
Completion questionnaire	Secondary	See study matrix Appendix B
Care home survey	Secondary	Appendix A

Study Matrix for case-control study

Measurements	At enrolment	Week 1	Week 2
	(after consent)		
Demographics	Х		
Height	Х		
Weight	Х		
Co-morbidities	Х		
Medications	Х		
Mini Nutritional	Х		
Assessment			
Food Menu	X		
Faecal Samples		Х	Х
Behavioural chart	Х		
DEMQOL in AD groups	Х		
Completion exit questionnaire			Х

4. Study Population

4.1. Number of Participants

- (i) with Alzheimer's dementia and challenging behavioural symptoms (n=20)
- (ii) with Alzheimer's dementia and no challenging behavioural symptoms (n=20)
- (iii) with no dementia (n=20)

4.2. Inclusion Criteria

Resident in a care home

4.3. Exclusion Criteria

- 1. Use of antibiotics in the last 8 weeks
- 2. Active gastrointestinal disease.
- 3. Unable to provide informed consent

5. Participant Selection and Enrolment

5.1. Identifying Participants

Research nurse will perform the initial approach to local care homes to determine whether they are willing to be involved in the study. This will be done first by contacting care homes by telephone and follow up visit or post to the care home with the study information package. At this point the care home manager will be asked to identify individuals within each care home who may fall into one of the three study groups. These individuals (or their carer, legal guardian or person with power of attorney) will be approached to see if they are interested in participating in the study. If they were interested to speak to research team, then the research nurse will explain about the study and give study information for them to consider the study participation.

5.2. Consenting Participants

Consent will be taken by the study research nurse who has appropriate training. Consent will be recorded appropriately on the study consent form.

For end of study questionnaire, participants' consent will be taken specifically.

5.3. Screening for Eligibility

In order to be recruited into study group (i) or (ii) there has to be an existing medical diagnosis of Alzheimer's dementia that will be confirmed by cross-referencing with medical records. Likewise for recruitment to group (iii) no such diagnosis should exist. The sub-group stratification of Alzheimer's dementia patients with or without behaviours that are challenging will be ascribed after speaking to care home staff and analysing care home records of participants.

Eligibility will be determined based on the knowledge of care home manager and staff. At this stage, the research team will not have any knowledge of who they are. Potentially eligible participants will first be approached by care home manager/staff to enquire whether they would be willing to speak to research team. Only those who are willing to speak to research team will be approached by the research nurse and provide study information. If they are interested and provide permission to check the eligibility, the diagnosis will be checked against their care home records. In case if the care home staff deem the potential participant lacks capacity, formal capacity assessment will be carried out by medically trained research team member.

Initial screening for eligibility will be carried out by care home staff and second level screening by study team will only happen after the participant has provided informed verbal consent prior to participation. If eligible written informed consent will be taken for study procedures.

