Changes in dietary composition and diversity were considered the main drivers of the shifts in gut bacteria profile. In this multi-disciplinary research study, we will investigate the gut microbiota composition in people with Alzheimer's dementia with challenging behaviours, test the feasibility of recruitment, and provide initial data to support a future grant application involving a dietary intervention study in patients with Alzheimer's disease.

We will test our hypothesis that the gut-brain axis promotes behavioural changes in Alzheimer's dementia and is responsive to changes in gut microbiota profile, by comparing the gut microbiota profile between three participant groups (1) Alzheimer's dementia with challenging behaviour, (2) Alzheimer's dementia without challenging behaviour, and (3) a control group of healthy age-matched elderly. We will also carry out a survey to care homes to assess their willingness to participate in dietary supplementation study.

1. Introduction

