2.1. Objectives

2.1.1. Primary Objective

To compare the composition and activity of the gut microbiota in three groups of elderly individuals: (i) Alzheimer's dementia and challenging behavioural symptoms, (ii) Alzheimer's dementia and no challenging behavioural symptoms, (iii) and people without dementia of any type.

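### Group (iii) is defined by the absence of a recorded diagnosis, with no check of cognition, so residents with undiagnosed dementia can enter the no-dementia control group

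*Combined protocol and SAP*

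**What the plan says.** Section 2.1.1 defines the third group as "people without dementia of any type". Sections 3.1 and 4.1 agree that group (iii) has no dementia, and the opening summary goes further with "a control group of healthy age-matched elderly".

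Section 5.3 sets the operational rules. For groups (i) and (ii), "there has to be an existing medical diagnosis of Alzheimer's dementia that will be confirmed by cross-referencing with medical records". For controls, "Likewise for recruitment to group (iii) no such diagnosis should exist". The source of the decision is given as "Eligibility will be determined based on the knowledge of care home manager and staff". After the resident gives permission, "the diagnosis will be checked against their care home records".

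The only inclusion criterion in 4.2 is care home residence. Section 4.3 excludes anyone who cannot give informed consent, in all three groups. Section 5.3 adds a conditional step: "In case if the care home staff deem the potential participant lacks capacity, formal capacity assessment will be carried out".

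The study matrix in 3.2 lists no cognitive test for any group. DEMQOL measures quality of life and is taken only in the Alzheimer's groups. Sections 9.2 and 9.3 contain no sensitivity analysis for controls who may be misclassified.

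**The concern.** A missing diagnosis is weaker evidence than a confirmed one. Cases enter on a positive entry in the record. Controls enter because no entry is found, in a care home population where intact cognition cannot be presumed. Undiagnosed dementia would leave no entry to find.

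If some controls have undetected dementia and a gut profile like that of the Alzheimer's groups, group (iii) moves towards groups (i) and (ii). Two of the three pairwise contrasts in the primary outcome involve group (iii). A null result on either could mean that there is no difference, or that the control group was mixed. Because nothing about cognition is recorded for controls, no later analysis could separate the two. The summary says these data are to support a grant application for a dietary intervention study, so the distinction matters.

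**Working it through.** **Definition against rule.** In 5.3 the word "such" in the control rule follows a sentence about a medical diagnosis of Alzheimer's dementia. Taken literally, a resident with recorded vascular dementia, for example, meets the rule for group (iii) but not the definition in 2.1.1, 3.1 or 4.1.

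**Do the existing safeguards close the gap?** The consent exclusion and the conditional capacity assessment may remove severe undiagnosed cases. But groups (i) and (ii) must meet the same consent requirement. A requirement that people with diagnosed Alzheimer's dementia are expected to meet cannot show that those who meet it have no dementia.

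**The plan's power figure.** Section 9.1 states at least 90% power with 20 volunteers for a 20% shift in SCFA and metabolites and a 45% difference in bacteria. It gives no standard deviation, significance level or test, so the figure cannot be reproduced. I take 90% as the baseline and solve for the effect that gives it.

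**Assumptions (not in the documents).** Two-sided 0.05 two-sample t-test with 38 degrees of freedom; share p of group (iii) with undetected dementia; each such resident carries a fraction f of the Alzheimer's-minus-control difference.

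1. With 20 per group, 90% power needs a standardised difference d = 1.052. The implied SD is 20/1.052 = 19.0% for SCFA and 45/1.052 = 42.8% for bacteria.
2. Expected contrast = d × (1 − p·f).
3. Variance in group (iii), in units of the common variance = 1 + p(1 − p)(f·d)².
4. Effective d = contrast ÷ √[(1 + that variance)/2]. Power comes from the noncentral t with noncentrality effective d × √(20/2).

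Example, p = 20%, f = 1: contrast 1.052 × 0.8 = 0.842; variance 1 + 0.16 × 1.107 = 1.177; effective d = 0.842/1.043 = 0.807; power 70%.

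Example, p = 20%, f = 0.5: contrast 1.052 × 0.9 = 0.947; variance 1 + 0.16 × 0.277 = 1.044; effective d = 0.947/1.011 = 0.936; power 82%.

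| Share p (of 20) | Power, full profile | Power, half profile |
|---|---|---|
| 0 | 90% | 90% |
| 5% (1) | 86% | 88% |
| 10% (2) | 81% | 86% |
| 20% (4) | 70% | 82% |
| 30% (6) | 57% | 78% |

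Leaving out the added variance in step 3, the full-profile column reads 87%, 83%, 74% and 62%.

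On the plan's own scale, at p = 20% a true 20% SCFA shift is expected to appear as 20 × 0.8 = 16% with the full profile, or 20 × 0.9 = 18% with half. A true 45% bacterial difference appears as 36% or 40.5%.

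**The case against.** The case for leaving the plan alone has five parts.

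- **The negative is checked.** Staff screen first, and the study team then consults records. A reader might infer that absence of dementia is simply assumed; 5.3 does not support that. What is missing is any check beyond the record. The diagnoses in groups (i) and (ii) are also record-based and not retested.
- **No rate is given.** A reader might infer that undiagnosed residents will enter group (iii). The documents support only that they can.
- **Shrinkage is not assured for every contrast.** It depends on undetected cases resembling the group they are compared with. If groups (i) and (ii) lie on opposite sides of controls for some taxon, contamination could narrow one contrast and widen the other.
- **The full profile is a pessimistic assumption.** Residents whom staff and records have not identified, and who can consent, may well be milder cases. The half-profile column is there for that reason. The 90% baseline is itself uncertain: 9.1 refers to volunteers on a controlled diet, which this study does not impose.
- **The consequence is limited.** The Rationale for Study puts first the difference between Alzheimer's patients with and without challenging behaviour, and that contrast is untouched. The study is also meant to give initial data and test feasibility.

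These points limit the certainty and size of the concern. They do not supply the missing check, and they do not reconcile the rule in 5.3 with the definition in 2.1.1.

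**Conclusion.** The concern holds in this form: the rule for group (iii) does not establish what the primary objective requires, and the plan has no means of judging afterwards how far the group departs from its definition. The literal wording of 5.3 also conflicts with 2.1.1, 3.1 and 4.1, and these sections must be reconciled.

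For contamination between 5% and 30%, power on a control contrast would fall from 90% to somewhere between 88% and 57%, depending on the share and on how closely undetected cases resemble the Alzheimer's groups. The share, the resemblance, the test and the 90% baseline are all assumptions, so this is a range of consequences and not an estimate. A reader might go further and infer that the control comparison is invalid, or that every contrast is biased to null; the documents support neither. The design stands. The change is worth making because it is cheap and affects what a null control contrast can be taken to mean.

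**What to change.** 1. In 5.3, state that group (iii) requires no recorded diagnosis of dementia of any type, in line with 2.1.1, 3.1 and 4.1.
2. At enrolment, record for each control any documented or staff-reported memory or cognitive problem, and add this to the study matrix in 3.2. Staff and records are already consulted, and co-morbidities are already collected at that point.
3. In 9.2, pre-specify a sensitivity analysis of the primary comparison without those controls.

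A brief cognitive measure at enrolment is an optional addition. It should inform the sensitivity analysis and not act as a hard exclusion: a positive screen is not a diagnosis, a cut-off could select unusually intact controls, and enrolment measurements come after consent, so a cut-off would remove people already recruited.

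Cost: a few minutes of recording per control, a smaller group (iii) in the sensitivity analysis, and an amendment needing sponsor, REC and R&D approval under 13.1. Without the optional measure, problems unknown to both staff and records would still be missed, so the analysis reduces the ambiguity but does not remove it.

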5.4. Ineligible and Non-Recruited Participants

Only eligible volunteers will be recruited to the study, up to the required number in each group. Once this number is reached, any additional interested volunteers will be thanked for their interest. No data will be collected prior to recruitment.

6. Withdrawal Procedures

If any participant wishes to withdraw from the study at any point after recruitment, all data and samples collected will be destroyed. If the carer perceives that participation in the study is causing distress to the volunteer, they will provide advice but if the distress persists the volunteer may be withdrawn from the study. In both cases a 'withdrawn from study' form will be completed and attached to the CRF. Unless such a form is completed (by either the volunteer or their representative) and consent is thus withdrawn, all samples will be kept following appropriate study guidelines. As the study requires 20 participant in each arm of the study, we will replace the withdrawal with further recruitment.

7. Data Collection and Management

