1.1. Background

Healthy life expectancy is a key area of research. It has been estimated that 36 million people have dementia worldwide (Prince et al., 2013) and that there are 4.6 million new cases of dementia every year (Ferri et al., 2005). Epidemiological evidence supports the hypothesis that modifiable lifestyle-related factors are associated with cognitive decline, opening new avenues for prevention (Solfrizzi et al., 2008). Alzheimer's disease is the commonest cause of dementia in older people, accounting for 60–70% of all dementia cases when using traditional diagnostic criteria for dementia subtypes (Blennow et al., 2006; Fratiglioni et al., 1999).

There are no available cures for AD, but an alternative approach is to use strategies that delay disease progression at an early stage (Lobo et al, 2000). Optimal brain function results from highly complex interactions between numerous genetic and environmental factors, including food intake, physical activity, age and stress (Solfrizzi et al, 2008). Diet in particular has become the object of intense research in relation to cognitive aging and neurodegenerative diseases.

The gut microbiota is a large, diverse collection of microbes, collectively containing 100 times more genes than the host. It is host-specific, contains heritable components, can be modified by diet, surgery or antibiotics, and in its absence nearly all aspects of host physiology are affected (Marchesi et al, 2016). We now realise that the human microbiota is a previously overlooked system that makes a significant contribution to human biology and development. There is a new and exciting field of research with limited published data in the elderly (Mariat et al, 2009; Claesson et al, 2012), that could provide a basis for the design of novel, microbiota-targeted, therapies to improve care of older people who suffer from Alzheimer's dementia.

There is increasing evidence that identifies the gut microbiota as a key conduit between nutrition and brain function (Goyal et al., 2015). Reduction in the frequency of genes encoding short chain fatty acid (SCFA) production was prominent among institutionalized older adults, as were increases in circulating pro-inflammatory cytokines tumour necrosis factor-alpha, interleukins-6 and -8, and C-reactive protein (Claesson et al., 2012).

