3.1. Study Description

An observational case-controlled study with three groups of participants with 1:1:1 will be carried out. A total of 60 volunteers, 20 in each group from the following groups (i) Alzheimer's dementia and challenging behavioural symptoms, (ii) Alzheimer's dementia and no challenging behavioural symptoms, (iii) without any type of dementia, will be recruited from care homes.

Each volunteer (assisted by staff) will provide two faecal samples, at least a week apart which will be analysed for microbial composition and activity by assessing Short Chain Fatty Acid profile (SCFA profile). Faecal samples will be collected using a pot on a toilet/commode, which will be sealed and processed in the laboratory within 12hr.

Additional information on regular diet composition will be collected by accessing the weekly care home menu. Staff will observe participants and record every episode which requires staff intervention as a result of behaviours that are challenging to manage.

A quality of life questionnaire will be completed by each volunteer in Alzheimer's dementia groups using DEMQOL (Dementia Quality of Life questionnaire).

DEMQOL is widely used patient reported outcome measures (PROMs) of health related quality of life in people with dementia.

Finally, we will collect other information on medication, personal characteristics, co-morbidities etc. to mitigate any confounding effects.

To achieve the secondary objectives the following outcomes will be assessed.

We will collect information on the following key aspects of feasibility of a larger study (future clinical trial) based on the main hypothesis driven work carried out under aim 3 described below

- (1) Proportion of eligible older people with Alzheimer's dementia with or without challenging behaviours
- (2) Proportion of eligible participants willing to participate
- (3) Proportion of participants who are able provide samples in each group
- (4) Proportion of participants (staff who are looking after them or relatives) who are able to provide study data /information

We will assess participants, their carers and whenever relevant managers and staff of care home and relatives/family members and people with Alzheimer's dementia with regard to willingness to participate in a research trial and to identify issues to be addressed to gain support for such an intervention trial through end of study questionnaire conducted by the study research nurse face to face.

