9.3. Missing Data

The two time points in this study will be used to show consistency of microbial profiles within an individual. If there are missing data points then a reduced dataset of the double time points will be analysed, and an additional analysis of single time points will be made. Having double collection times from each individual will also test the feasibility of the collection process for the main study. We will collect menus from both weeks preceding sample collection in order to have some dietary record in the immediate run-up to sample collection.

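### Group quotas ignore care home and the planned comparison has no home term, so if the groups fall unevenly across homes a home effect can pass for a dementia or behaviour effect

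*Combined protocol and SAP*

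**What the plan says.** **Recruitment.** Section 3.1 states the design: "An observational case-controlled study with three groups of participants with 1:1:1 will be carried out". It takes 20 people per group, all from care homes. Candidates are found through the homes; under section 5.1, "the care home manager will be asked to identify individuals within each care home who may fall into one of the three study groups". Section 5.4 sets the quota: "Only eligible volunteers will be recruited to the study, up to the required number in each group". Section 6 replaces withdrawals by further recruitment. None of these sections balances, caps or matches the groups by home. The sole inclusion criterion in section 4.2 is "Resident in a care home". Length of stay is neither a criterion nor an item in the study matrix (section 3.2).

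**Diet.** The summary before section 1 says: "Changes in dietary composition and diversity were considered the main drivers of the shifts in gut bacteria profile". On measurement, section 3.1 says: "Additional information on regular diet composition will be collected by accessing the weekly care home menu". Section 9.3 adds: "We will collect menus from both weeks preceding sample collection in order to have some dietary record". The matrix also lists a Mini Nutritional Assessment. Section 7.1 mentions food diaries among the stored papers, but no section schedules one.

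**Analysis.** Section 9.2 plans descriptive summaries and parametric or non-parametric comparisons of the three groups. It names no covariate, cluster or home term. Section 3.1 says that medication, personal characteristics and co-morbidities are collected to deal with confounding; home is not named.

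**The concern.** A menu describes a home, not a resident, so everyone sampled in one home has the same scheduled diet record. With quotas set per group and not per home, residents with challenging behaviour could come mainly from some homes and controls mainly from others. The group comparison would then also be a comparison of menus, and of anything else that differs between homes.

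That comparison is the primary objective (section 2.1.1), and the summary intends the data to support a grant application for a dietary intervention. A false lead would carry forward. The power statement in section 9.1 refers to volunteers on a controlled diet. This observational study does not control diet, so the spread of groups over menus matters more here than in the data behind that statement.

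**Working it through.** **The plan's own figure.** Section 9.1 claims at least 90% power with 20 volunteers for a 20% shift in SCFA and a 45% difference in bacteria. It gives no SD, significance level or test, so the figure cannot be reproduced. One can only solve for what it implies. With 20 per group and two-sided 5% (assumed), the standardised difference is d = (1.960 + 1.282) × √(2/20) = 1.025. The implied coefficients of variation are 20/1.025 = 19.5% for SCFA and 45/1.025 = 43.9% for bacteria.

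**Assumptions for the home effect.** The documents give neither the number of homes nor a between-home intraclass correlation (ICC). I take an ICC of 0.1 to 0.2, total variance 1, no true group difference, and a one-way ANOVA at 5% on 3 × 20 people.

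**Case 1: each home supplies one group only.** With k homes per group:
- the between-group mean square is inflated by D = 1 + (20/k − 1) × ICC;
- the expected within-group mean square is W = (20 − D)/19;
- the critical value of F(2, 57) is 3.159, and P(F > x) = (1 + 2x/57)^(−28.5);
- the false-positive rate is approximately P(F > 3.159 × W/D).

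| Homes per group | ICC | D | 3.159 × W/D | Formula | Simulation (20,000 runs) |
|---|---|---|---|---|---|
| 4 | 0.1 | 1.4 | 2.21 | 11.9% | 12.1% |
| 4 | 0.2 | 1.8 | 1.68 | 19.5% | 19.1% |
| 2 | 0.1 | 1.9 | 1.58 | 21.4% | 21.5% |
| 2 | 0.2 | 2.8 | 1.02 | 36.7% | 36.8% |

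Repeat simulations vary by about one percentage point. Smaller ICCs or more homes soften this: with four homes per group, 6.2% at ICC 0.02 and 8.2% at 0.05; with ten homes per group, 5.3% to 10.0% over ICC 0.02 to 0.30.

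**Case 2: four homes, all groups present, uneven numbers** (simulated):
- Moderate imbalance (7,6,4,3 / 5,5,5,5 / 3,4,6,7): 4% to 5% at ICC 0.05 to 0.2, so no inflation.
- Strong imbalance (9,7,3,1 / 5,5,5,5 / 1,3,7,9): about 6%, 7% and 9% at ICC 0.05, 0.1 and 0.2.
- With home as a factor in the model, both layouts return to about 5%.

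**Case 3: a systematic difference between two kinds of home.** This is harsher: the kinds are assumed to differ by 20% in SCFA, the whole shift the study is sized for. Bias = (difference in group shares) × 20%. An 80/20 against 20/80 split gives 0.6 × 20% = 12%. The standard error is 19.5% × √(2/20) = 6.17%, so z = 1.95 and an unadjusted two-group test has p < 0.05 about 49% of the time. A 60/40 against 40/60 split gives 4% and about 10%.

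**Case 4: equal numbers of each group in every home.** The unadjusted test is not inflated (2.0% to 5.3% over all settings tried). With home in the model the error is 4.6% to 5.3%. Power of the three-group F-test for one group shifted by d = 1.025 is 93% to 96% (ICC 0.05 to 0.20; 4 or 10 homes).

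**The case against.** The strongest reply is section 5.1. Managers look for all three groups in each home, so the described search points towards overlap, and Case 1 is an extreme. This stands: the bias is possible, not established. But the search does not require overlap, and section 5.4 closes each group on its overall count alone.

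Several stronger readings are tempting, and the documents do not support them.
- *Uneven recruitment cannot be repaired afterwards.* This is true only if groups and homes separate completely or nearly so. With overlap, Case 2 shows that a home term suffices. With complete separation a fixed home term leaves no group contrast to estimate. A random home effect would allow for chance variation between homes but not for a systematic difference in kind of home.
- *Diet is known only through the menu.* The menu is the only scheduled measure of diet composition. The food diaries in section 7.1 are unscheduled, and the Mini Nutritional Assessment is also taken.
- *The plan itself declares diet dominant in this population.* The summary sentence is in the past tense and may report earlier work. Section 1.1 also lists heritable components, surgery and antibiotics as influences.
- *Recent arrivals invalidate the comparison.* Section 1.1 notes: "Reduction in the frequency of genes encoding short chain fatty acid (SCFA) production was prominent among institutionalized older adults". But all three groups live in care homes, which largely removes that contrast. A new arrival may not have eaten the menus recorded, yet the documents offer no size for this and no basis for a particular minimum stay.

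It can also be said that this is a small study meant to give initial data. That limits the weight of any result, but the three-group comparison is still the primary objective.

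**Conclusion.** The point holds in this form: neither recruitment nor analysis controls for care home, so a home effect can appear as a dementia or behaviour effect. How far depends on how the groups happen to spread. At assumed ICCs of 0.1 to 0.2, the error of the unadjusted 5% test runs from no inflation (moderate imbalance), through about 7% to 9% (strong partial imbalance), to about 12% to 20% or 22% to 37% (complete separation, with four or two homes per group). The ICCs, the numbers of homes and the layouts are all assumptions, so these figures show a range and are not estimates for this study. The analysis gap can be closed whenever groups overlap within homes. Only recruitment can prevent complete separation.

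**What to change.** - **Sections 5.1 and 5.4:** recruit all three groups from the same homes as far as possible, and in particular groups (i) and (ii) within the same homes. Apply this to replacements under section 6 too.
- **Section 3.2:** record home and admission date. Use length of stay descriptively or in a sensitivity analysis, not as a fixed eligibility threshold. Reconcile the food diaries in section 7.1 with the matrix.
- **Section 9.2:** include home as a blocking factor or random effect in the group comparison.

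A looser rule that accepts any home with one dementia group plus controls would not do. If (i) and (ii) sit in different homes, each is compared with about 10 controls. The variance factor of their contrast is then 2 × (1/20 + 1/10) = 0.30, against 2/20 = 0.10 when they share homes. At d = 1.025 and ICC 0.1 to 0.2, power falls to about 49% to 53%, from 92% to 95%.

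The cost is an amendment to the wording, possibly somewhat slower recruitment, and a few degrees of freedom. Under the assumptions above, balance by home with home in the model loses no power. The recruitment change must be made before the groups fill.

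### Two promised feasibility proportions, eligible and willing among eligible, have no described source for their pre-recruitment counts, and section 5.4 read literally rules one out

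*Combined protocol and SAP*

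**What the plan says.** Section 3.1 commits the study to the feasibility measures in these words: "We will collect information on the following key aspects of feasibility of a larger study". The first of the four begins "Proportion of eligible older people with" Alzheimer's dementia, whether or not their behaviour is challenging. The second is "Proportion of eligible participants willing to participate". The third and fourth concern people already in the study (able to give samples, able to give study information).

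The early steps belong to the homes. Under 5.1 the "care home manager will be asked to identify individuals within each care home who may fall into one of the three study groups". Under 5.3, "Initial screening for eligibility will be carried out by care home staff", and staff also make the first approach. Of the people considered then, 5.3 says: "At this stage, the research team will not have any knowledge of who they are". The research nurse meets only those who agree to talk, and "second level screening by study team will only happen after the participant has provided informed verbal consent".

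Section 5.4, headed for ineligible and non-recruited participants, fills each group to its required number and thanks any further volunteers. It then says: "No data will be collected prior to recruitment". It makes no exception for anonymous counts.

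**The concern.** Measure (2) needs the eligible people who said no. They appear only before recruitment and never enter the study. Measure (1) needs the number of residents considered, which also exists only at that stage. Section 5.4 is where one would expect a screening log; it says instead that nothing is collected.

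The summary ahead of section 1 names recruitment feasibility and support for a later grant application as purposes of the study. If 5.4 is followed to the letter and the counts are held nowhere else, two of the four named measures cannot be computed. The later trial would then lack this study's estimate of how many residents must be considered or approached per recruit. If homes are not asked to count as they go, the figures may be hard to reconstruct reliably afterwards.

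**Working it through.** The plan gives no target, precision or denominator for either measure, so there is no stated figure to reproduce. The check is a search for a source, then an illustration of why the visible numbers do not replace it.

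**Step 1: where could the counts come from?**

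- Section 5.1: managers identify candidates. No instruction to count or report.
- Section 5.3: staff screen and approach. No record of outcomes or refusals is described.
- Section 3.2, study matrix: the first column is enrolment, after consent. There is no screening column.
- Sections 7.1 and 7.2: CRFs under a participant code, food diaries and questionnaires. No screening log.
- Section 3.1 and Appendix B: the completion questionnaire comes after sampling, so it cannot count those who declined.
- Section 10.2: the master file covers volunteers recruited.
- Appendix A, care home survey: content not available. The summary describes it as assessing homes' willingness. Section 3.2 maps it to the secondary objective, and 9.2 analyses it descriptively for the secondary objectives. Neither mentions resident counts.

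**Step 2: can the number recruited stand in?** Sections 3.1 and 4.1 fix it at 20 per group, 3 × 20 = 60. The eligible counts below are assumptions; the documents give none. Intervals are exact (Clopper-Pearson) 95%.

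| Assumed eligible | Recruited / eligible | 95% interval | Eligible per recruit |
|---|---|---|---|
| 80 | 60/80 = 75% | 64% to 84% | 80/60 = 1.3 |
| 300 | 60/300 = 20% | 16% to 25% | 300/60 = 5.0 |

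The intervals do not overlap, yet both rows have the same 60 recruits.

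Now take one group with 40 eligible residents, all approached (assumed), and count only the 20 recruited as willing:

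| Assumed truly willing | True proportion | Recruited / eligible | Shortfall |
|---|---|---|---|
| 30 | 30/40 = 75% | 20/40 = 50% | 25 points |
| 25 | 25/40 = 62.5% | 20/40 = 50% | 12.5 points |
| 20 | 20/40 = 50% | 20/40 = 50% | 0 |

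The shortfall comes from the cap: (willing − 20)/40.

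**Step 3: can the people the team screens serve as the denominator of (2)?** By the order of steps in 5.3 they have agreed to speak to the team and given verbal consent. Earlier refusals are missing, so the group is selected towards willingness. The size of that selection cannot be derived from the documents.

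**Step 4: which denominator would work for (2)?** Not all residents whom staff judge eligible. Once a group is full, those never approached would count as unwilling. With assumed counts of 80 judged eligible, 40 approached and 30 willing, 30/80 = 37.5% whereas 30/40 = 75%. The denominator has to be those actually approached.

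**The case against.** The strongest reply is that 5.4 was never meant to exclude counts. Section 7.2 speaks of data as records held under a participant's code. Section 5.3 has the diagnosis checked against care home records, and capacity formally assessed where needed, before written consent, so some information is plainly handled before enrolment. Section 3.1 says outright that the feasibility information will be collected. Reading 5.4 as a bar on individual-level data reconciles all three. This reply largely stands: a reader might infer that the protocol forbids its own outcome, and the text does not compel that. What remains is that no tally, form or responsible person is described, and that 5.4 as worded points the other way.

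The second reply is the Appendix A survey, a home-level instrument tied to the secondary objective in 3.2 and 9.2. It might hold the counts. That cannot be settled without the appendix, and its unavailability here is not a fault in the plan. Nothing said about the survey elsewhere mentions numbers of residents.

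Third, a reader might infer that willingness among people confirmed eligible by the team must come out at 100%. That is too strong: under 5.3 someone who gave verbal consent and passed the check can still decline written consent.

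Fourth, the shortfalls shown in the working arise only if the recruited number is used as the number willing, which no section proposes. Surplus volunteers who come forward could be counted. This is fair; the tables show what the recruited number cannot tell us, not an error the plan commits to.

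**Conclusion.** The point holds as a minor one. Section 3.1 promises two proportions, the supplied text names no source for the counts they need, and 5.4 taken literally excludes collecting them. Neither the capped number recruited nor the already willing group that the team screens can replace those counts.

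The size cannot be estimated from the documents. On assumed counts, the fixed 60 recruits fit anything from 1.3 to 5 eligible residents per recruit. The conclusion rests on the supplied text alone and would shrink to a missing cross-reference if Appendix A records these numbers.

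Two wider readings are not supported. One is that the feasibility outcome as a whole fails: measures (3) and (4) concern people in the study, and the secondary objective in 2.1.2, the willingness of homes and carers, is served by the survey and the face-to-face questionnaire. The other is that the microbiota comparison is weakened: it uses recruited participants only and is untouched. No progression threshold in the plan depends on (1) or (2).

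**What to change.** Replace the sentence in 5.4 with wording such as:

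> No individual-level or identifiable data will be collected before recruitment. Each home will keep an anonymous tally by study group of residents considered, judged potentially eligible by staff, approached, willing to speak to the team, found ineligible at the team's check, willing but group already full, and consented. Totals will be pooled across homes.

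If the Appendix A survey already captures these counts, cite it in 5.4 instead.

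In 3.1, define:

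- **(1)** as residents judged potentially eligible over residents considered. As worded, it could also mean the split by behaviour among those eligible.
- **(2)** as those willing, including those willing when the group was already full, over potentially eligible residents actually approached. Residents never approached because the group was full are left out, and those later found ineligible are reported separately.

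Measures (3) and (4) need no change for this point, and the destruction of withdrawn participants' data and samples under section 6 is unaffected.

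The cost is an amendment approved by the Sponsor, the REC and NHS R&D under 13.1, and a short running tally for home staff. Because the tally is anonymous and pooled, the protection of identity in 5.3 is kept.
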